1.2 Rationale of the study

Patients with osteosarcoma recurrence or metastases after initial therapy have 5 year overall survival of 16%. The median survival after 1st, 2nd, 3rd, or 4th recurrence was about 1 year [1] Although chemotherapy may possibly contribute to longer overall survival after first relapse, surgery is critical to prevent subsequent relapses. Thus for patients with axial, recurrent, or metastatic osteosarcoma, more effective treatments are needed. Ra-223 dichloride is an alpha-emitting radiopharmaceutical developed by Oyvind Bruland at the Norwegian Radium Hospital in Oslo (figure 1).

The intrinsic bone targeting property of Ra-223 dichloride is similar to calcium and other alkaline earth elements. Tables 2 and 3 show how the ^{223}Ra alpha-particle emitting radiopharmaceutical has different radiation dose characteristics than the current FDA approved beta-emitting radiopharmaceuticals such as $^{89}\text{SrCl}_2$ and $^{153}\text{Sm-EDTMP}$ [2]. Despite experience with $^{153}\text{Sm-EDTMP}$ for treatment of high-risk osteosarcoma [3-8], Radium-223 dichloride may have very significant advantages (less marrow toxicity and repeated dosing without stem cell support possible) compared to $^{153}\text{Sm-EDTMP}$. Radium-223 dichloride emits alpha-particles with high energy and high linear energy transfer (LET) radiation with a range limited to less than 100 micrometers. These radiation characteristics have the advantages of generating highly localized and effective radiation kill zones via the high probability of the dense alpha particles inducing double-strand breaks to the DNA of cancer cells.

In contrast, the ^{89}Sr and ^{153}Sm emit beta-particles (electrons) that have much lower energy and lower LET. Beta radiation mainly induces single-strand breaks to DNA which are more easily repaired. In addition, beta-particles typically have 30-80 times longer radiation range compared to alpha-particles. Thus, nearby tissues are more subject to collateral damage from beta-emitters. For example after radiation from beta-emitters, nearby marrow and stem cells are damaged resulting in anemia, leucopenia, and thrombocytopenia.

Rationale for dose level being studied

Ra-223 has been extensively studied in prostate cancer, with a median age of > 65. Osteosarcoma occurs in adolescent and young adults and for this type of disease, an osteoblastic bone-forming tumor, perhaps a higher dose would have a better efficacy in terms of its direct bone targeting properties. Because of low marrow toxicity of this radiopharmaceutical, knowledge of the recommended dose in this patient population is needed to develop future protocols.

[figure not shown]

Figure 2. Decay cascade of Ra-223. The initial ejection of the high LET alpha particle takes a relatively long time ($t=11.4$ days). Subsequent quick decay of radon daughters provide additional alpha particles quickly with for increased therapeutic effectiveness at target location of emission (bone-forming tumor cell in the case of osteosarcoma) and little changece for diffusion of radon daughters to other locations/tissues for non-target effects.

1.3 Ra-223 dichloride

1.3.1 Preclinical

In single and repeated dose toxicity studies in rats, the main findings were reduced body weight gain, hematological changes, reduced serum alkaline phosphatase and microscopic findings in the bone marrow (depletion of hematopoietic cells, fibrosis), spleen (secondary extra-medullary hematopoiesis) and bone (depletion of osteocytes, osteoblasts, osteoclasts, fibro-osseous lesions, disruption/disorganization of the physis/growth line). These findings were related to radiation-induced impairment of hematopoiesis and a reduction of osteogenesis and occurred beginning in the dose range of 20 (0.00056 mCi) – 80 kBq (0.0022 mCi) per kg body weight, with the exception of body weight decreases. ^{1 2}

Dose-limiting myelotoxicity was seen in dogs after single administration of 450 kBq (0.012 mCi) Ra-223 dichloride per kg body weight (9 times the clinically recommended dose).

Osteosarcomas, a known effect of bone-seeking radionuclides, were observed at clinically relevant doses in rats 7 – 12 months after start of treatment.

Osteosarcomas were not observed in dog studies. No case of osteosarcoma has been reported in clinical studies with Ra-223 dichloride. The risk for patients to develop osteosarcomas with exposure to Ra-223 dichloride is unknown at present.^{3 4 5}

Studies on reproductive and developmental toxicity have not been performed. Since Ra-223 dichloride binds to bone, the potential risk for toxic effects in the male gonads in cancer patients with castration-resistant prostate cancer is very low, but cannot be excluded. Studies on the mutagenic and carcinogenic potential of Ra-223 dichloride have not been performed.

No histological changes were observed in organs involved in the excretion of Ra-223 dichloride. No significant effects were seen on vital organ systems, i.e. cardiovascular (dog), respiratory or central nervous systems (rat), after single dose administration of 450 to 1000 kBq (0.012 to 0.027 mCi) per kg body weight (9 (dog) to 20 (rat) times the clinically recommended dose).

1.3.1 Pharmacokinetics / pharmacodynamics

No PK or PD studies are proposed. See Investigator's brochure.

1.3.2 Clinical Experience Summary

The clinical development of Ra-223 dichloride, to date, includes nine studies in patients with prostate cancer or breast cancer with bone metastases. The Phase I program consisted of three studies to establish the safety, dose limiting toxicities, dosimetry, biodistribution and PK in patients with bonemetastases mainly from prostate cancer; and it included some patients with MBC with bone metastases. The Phase II program included three completed studies of Ra-223 dichloride in patients with prostate and breast cancer, who have bone metastases. The results of the completed studies indicated that safety and tolerability of Ra-223 dichloride in CRPC/HRPC patients with bone metastases was well tolerated, and that there was evidence of dose related efficacy against bone markers and other markers of disease. In addition there was an effect on median overall survival in a Phase II (BC1-02) placebo-controlled study. These studies enabled the initiation of the Phase III ALSYMPCA (ALpharadin in SYMptomatic Prostate CANcer) study.

The clinical safety and efficacy of Ra-223 dichloride have been evaluated in a double-blind, randomized, multiple dose, phase III multicenter study (ALSYMPCA) in castration-resistant prostate cancer patients with bone metastases. The primary efficacy endpoint was Overall Survival (OS).

At the cut-off date of the pre-planned interim analysis, a total of 809 patients were randomized 2:1 to receive Ra-223 dichloride 50 kBq (0.0014 mCi)/kg intravenously every 4 weeks for 6 cycles (N=541) plus best standard of care or matching placebo plus best standard of care (N=268). Best standard of care included e.g. local external beam radiotherapy, corticosteroids, antiandrogens, estrogens, estramustine or ketoconazole.

An updated descriptive analysis of safety and of OS was performed in 921 randomized patients prior to implementing crossover (i.e. offering patients in the placebo group to receive Ra-223 dichloride treatment).

The results of both, interim and updated analysis, revealed that OS was significantly longer in patients treated with Ra-223 dichloride plus best standard of care compared to patients treated with placebo plus best standard of care. For the updated analysis, an increase in median overall survival of 3.6 months was seen with Ra-223 dichloride plus best standard of care compared to placebo plus best standard of care (HR =0.695 (95% CI 0.581/0.832), median OS 14.9 months versus 11.3 months, respectively).

The results of the interim analysis and the updated analysis showed also a significant improvement in all main secondary endpoints in the Ra-223 dichloride arm compared to the placebo arm:

Time to SRE (to be update based on final results) - As with good practice, the sponsors have conducted further verification of the ALSYMPCA SRE data in preparation for the US FDA NDA regulatory submission. This has resulted in changes in the numbers previously reported for SRE data in the ASCO 2012 abstracts (Abstract #4551, LBA #4512). Though discrepancies were noted, the overall interpretation of the results has not changed. The SRE data will be disclosed once all additional data verification and analyses activities are completed.”

Prolonging the time to total ALP progression (defined as $\geq 25\%$ increase compared to baseline/nadir) (Interim analysis: HR = 0.163, 95% CI 0.121 – 0.221; $p < 0.00001$, median number of months not estimable since median was not reached at the time of data cut-off; updated analysis: HR = 0.167, 95% CI 0.129 – 0.217; median number of months = 7.4 months for Ra-223 dichloride versus 3.8 months for placebo).

Time to PSA progression (defined as a $\geq 25\%$ increase and an increase in absolute value of ≥ 2 ng/mL compared to baseline/nadir) was also

significantly prolonged in patients receiving Ra-223 dichloride compared to patients receiving placebo (Interim analysis: HR = 0.671, 95% CI 0.546 – 0.826; p = 0.00015, median number of months = 3.6 months for Ra-223 dichloride versus 3.4 months)

Total ALP response (confirmed \geq 30% reduction compared to baseline) at week 12 compared to the placebo group (Interim analysis: 43.3% in the Ra-223 dichloride group, 2.5% in the placebo group, p < 0.001; updated analysis: 46.9% in the Ra-223 dichloride group, 3.3% in the placebo group).

Most common non-hematologic all grades adverse events occurring in more than 15% of patients were: bone pain (43% vs. 58%), diarrhea (22% vs. 13%), nausea (34% vs. 31%), vomiting (17% vs. 13%) and constipation (18% vs. 18%). Most common hematologic all grades adverse events were anemia (27% vs. 27%), neutropenia (4% vs. 1%) and platelets (8% vs. 6%).

Subgroup survival analysis

Subgroup survival analysis showed a consistent survival benefit for treatment with Ra-223 dichloride, independent of total alkaline phosphatase (ALP), current use of bisphosphonates, prior use of docetaxel and baseline ECOG status.

Pain relief

The results from the phase III ALSYMCA study regarding time to external beam radiation therapy (EBRT) for pain relief and fewer patients reporting bone pain as an adverse event in the Ra-223 dichloride group indicate a positive effect on bone pain. This is further supported by the effects seen on bone pain using specific pain measures in a single dose Phase II study.

2. Study objectives

- 2.1** Primary Objective: Determine maximum tolerated or recommended dose of monthly Ra-223 dichloride in patients with recurrent or metastatic osteosarcoma. Comparison of safety and toxicity of 50, 75, and 100 kBq Ra-223- dichloride /kg will be made.
- 2.2** Secondary Objectives: compare alkaline phosphatase reduction to quantitative imaging techniques (^{99m}Tc -MDP, ^{18}F FDG-PET-CT, ^{18}F Na PET-CT scans to determine objective response of osteosarcoma indicator lesions to 223-radium dichloride

3. Investigator[s] and other study participants

PI

[name] MD
MDACC Assistant Professor,
Investigational Cancer Therapeutics, [name]
[contact]; [contact]
[contact]

Co- PI and Ra-223 dichloride license holder: [name] MD
MDACC Associate Professor [name]
[name]; [contact] [contact]
[contact]

Other key personnel: [name] Senior Medical Physicist
[name] [contact]; [contact]
[contact]

[name], Professor, Biostatistics [contact]. [name]
[contact]

[figure not shown]
4. Study design

The goal of this initial study is to determine the safety of escalating doses of monthly Ra-223 dichloride in osteosarcoma patients with osteoblastic bone-forming metastases until MTD or a dose 100 kBq/kg dose is reached (whichever is first). Radium-223 dichloride will be given monthly for up to 6 cycles and side effects of this bone-targeted therapy on monthly blood counts and alkaline phosphatase will be determined. After 3 and 6 doses patients will have imaging to compare ^{99m}TcMDP uptake to baseline and other imaging as clinically indicated including ¹⁸F-FDG PET-CT, Na¹⁸F and/ chest CT. Anatomic imaging (CT or MRI) of all sites of disease along with chest CT at baseline and restaging for all patients will be done to allow for assessment of RECIST progression. RECIST progression will determine progressive disease regardless of other imaging.

Table 1. Ra-223 dichloride Dose Escalation scheme (N=3/cohort)

Dose level:	kBq/kg	N
-1	25	--
0 (starting dose)	50	3
1	75	3
2	100	8
Expansion cohort	MTD	6

Anticipated Total N = 9- 20 (N= 20 assumes reaching 100 mBq/kg MTD)

***Imaging:** Three modalities will be compared
pre vs after dose 3 and after dose 6
ΔSUV of ¹⁸F PET-CT
ΔSUV Na¹⁸F PET-CT
Δ activity ^{99m}Tc-MDP SPECT -CT

Table 2. Decay and Marrow/Bone Ratios Clinically Useful Bone-seeking Isotopes

	Half-life	*Ratio of Surface	Particle	MeV particle	Range
	Days	Bone : red marrow		Emission energy	(mm)
¹⁵³ Sm-EDTMP	2	4.4	Beta	0.66 max 0.22 average	0.6
⁸⁹ SrCl ₂	50.5	1.6	Beta	0.58	2.4
²²³ RaCl	11.4	10.3	Alpha	27.4	<0.1

* Bone surface to red bone marrow radioactivity dose ratio

Table 3. Comparison of Alpha and Beta Particles from Bone-Seeking Cancer Drugs

Characteristic	Alpha	Beta
Range (um)	40-90	50-6000
Linear Energy Transfer*	60-230	0.015-0.4

Relative mass	7000**	1**
DNA hits to kill a cell	1-5	100-3000
Cytotoxic against G ₀ cells	Yes	No
Effective against “radio-resistant” cells	Yes	No

*(LET; keV/μm)

**Alpha particles are dense particles (i.e. like a helium nucleus); beta particles are electrons

Preclinical work showed that mice had significantly less marrow toxicity from Ra-223 dichloride than after the beta-emitting radiopharmaceutical strontium-89 chloride [9, 10]. Alpharadin has shown promising marrow-sparing properties in patients with bone metastases of hormone refractory prostate cancer [2, 11, 12]. In a placebo controlled trial, patients with hormone refractory prostate cancer bone metastases had no significant effects on blood counts after repeated monthly Ra-223 dichloride doses (50kBq/kg) [12].

Bone marrow suppression from Ra-223 dichloride has been minimal. Alkaline phosphatase in patients with prostate cancer bone metastases after ²²³Ra decreased was 66% versus increase of 9% in placebo treated patients (p=0.001) [12]. Time to PSA progression was 26 versus 8 weeks (p=0.048). A large phase III multicenter, randomized, double blinded, placebo controlled trial in prostate cancer is underway and includes centers in Europe and the USA [13]. Results of Alpharadin against prostate cancer bone metastases in two randomized phase II studies were reviewed at ASCO 2011 by Nielsson et al. [14]. Alkaline phosphatase normalization was dose-related in trial BC1-04: 5/29 (17% in 25 kBq/kg group, 10/25 (40%) in the 50kBq/kg group, and 10/21 (48%) in the 80 kBq/kg group. Alkaline phosphatase normalization was associated with significantly improved median survival (58 weeks vs 102 weeks (log rank p=0.0086).

Alkaline phosphatase is a marker not only of bone formation associated with metastases to bone in osteosarcoma, but also the intrinsic bone forming activity by the osteoblastic osteosarcoma neoplastic cells. Mialou et al. found that not only bone (vs lung) metastases, but also high alkaline phosphatase (>500 IU) was significantly associated with a worse outcome in metastatic osteosarcoma [15]. An alpha-emitting targeted radiopharmaceutical located in osteosarcoma target tissue will deliver the radiation to a much more localized tumor volume than a beta-emitter, thereby reducing exposure of surrounding normal tissues and leading to less toxicity.

Thus a dose finding study to determine best dose for monthly Alpharadin dosing in osteosarcoma is proposed. This information can then be used to develop potential “game-changing” strategies against osteosarcoma to improve pain in metastatic patients, make surgery better (fewer amputations, better function), and reduce the considerable morbidity of current therapy,

5. Study population

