Diagnosis and main criteria for inclusion	Osteosarcoma with 1) metastatic or recurrent disease and 2) indicator lesion(s) avid on ^{99m} Tc-MDP bone scan.
Study design	The study design is a 3+3 Phase I dose escalation (N=3/cohort) with expansion at highest safe dose (N=6); if 75kBq is 2/3 DLT, the dose -1 (50kBq/kg) is the MTD
Type of control	Uncontrolled study (i.e. no placebo or control group)
Number of subjects	Dose escalation N=14; dose expansion N=6 ;total= 20
Plan for statistical analysis	
Primary objective: Determine maximum tolerated or recommended dose of monthly 223-radium dichloride in patients with recurrent or metastatic osteosarcoma. Comparison of safety and toxicity of 50, 75, and 100 kBq 223-radium dichloride /kg will be made.
 
Secondary Objectives: Analysis change in objective measurements of alkaline phosphatase pre , before dose 4 (mid study) and at end of study (after dose 6) vs change in SUV of for PET- scans (¹⁸FDG and /or ¹⁸FNa) and of SPECT CT for ^{99m}Tc-MDP. Changes in uptake will be analyzed for dose response effects (between groups) and pre vs mid study and end of study (within group)

List of abbreviations

AE	Adverse Event
ALP	Alkaline Phosphatase
ALSYMPCA	Alpharadin in Symptomatic Prostate Cancer
ALT	Alanine Aminotransferase
ANC	Absolute Neutrophil Count
AST	Aspartate Aminotransferase
BPI-SF	Brief Pain Index (Short Form)
BSoC	Best Standard of Care
CBC	Complete Blood Count
CRO	Clinical Research Organization
CRPC	Castration Resistant Prostate Cancer
CT	Computed tomography
CTCAE	Common Terminology Criteria for Adverse Events; version 4.03
DK	Decay Correction Factor
EBRT	External Beam Radiation Therapy
ECOG	Eastern Co-operative Oncology Group
eCRF	Electronic Case Report Form
EU	European Union
GCP	Good Clinical Practice
GCL	Global Clinical Leader
GMP	Good Manufacturing Practice
HRPC	Hormone Resistant Prostate Cancer
IB	Investigator Brochure
ICF	Informed Consent Form
ICH	International Conference on Harmonization
IDMC	Independent data monitoring committee
IEC	Independent Ethics Committee
IRB	Institutional Review Board
IV	Intravenous
IxRS	Interactive Voice/Web Response System (IVR/IVRS)
kBq	KiloBecquerel; SI Unit of Radioactivity
kg	Kilogram
LHRH	Luteinizing-Hormone-Releasing Hormone; also known as Gonadotropin-Releaseing Hormone (GnRH)
mCi	Millicuries
MedDRA	Medical Dictionary for Regulatory Activities
mL	Milliliter
MRI	Magnetic Resonance Imaging
NCI	National Cancer Institute
NYHA	New York Heart Association

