8.1 Analysis sets

Safety monitoring rule

- Should DLTs occur in more than two patients at any time during the dose expansion phase clinical personnel and study investigators will meet and assess the attribution, severity and nature of the DLTs. No additional patients will be accrued until the data is reviewed and a decision is made to continue at the current dose or to de-escalate the prior dose as the dose for the expansion phase. This review and decision will be documented in writing.

Monitoring of alkaline phosphatase

- Alkaline phosphatase, a biomarker associated with osteosarcoma metastases, will be determined monthly before administration of each dose of Ra-223 dichloride. The trend of improvement (or not) will be analyzed for a particular patient and number of patients in a cohort with improvement as a function of dose # will be analyzed.

Imaging

- Nuclear Medicine Studies will use commercially available ^{99m}Tc , ^{18}F Fluorodeoxyglucose and sodium ^{18}F Fluoride to image indicator lesions. The trend of improvement (or not) in ^{99m}Tc -MDP on SPECT CT, ^{18}F FDG-PET-CT SUV, or Na^{18}F SUV will be compared for study entry vs after dose #3 and study entry vs after dose #6 and after dose #3 vs after dose #6 will analyzed for a particular patient and number of patients in a cohort with improvement after dose #3 and dose #6 will be analyzed.
- Analysis of lung metastases. Up to 3 measurable (1 cm or larger) indicator lesions seen on chest CT may be described at study entry and compared after dose #3 and dose #6. RECIST criteria (>20% increase in size) will be used as criteria for progression. Any change <20% or if size is <1 cm will not be used for “off study” progression criteria.
- RECIST progression will determine progressive disease regardless of other imaging.

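### The promised dose comparisons rest on DLT proportions that the 3+3 rule restricts at passed levels and on per-cohort counts of improvement with no stated scale; continuous relative change over all dosed patients would use the data better.

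*Combined protocol and SAP*

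**What the plan says.** Section 2.1 (repeated in the synopsis) promises a "Comparison of safety and toxicity of 50, 75, and 100 kBq" per kg as part of the primary objective. The synopsis analysis plan adds: "Changes in uptake will be analyzed for dose response effects (between groups"). Section 2.2 itself makes no dose comparison; its aim is to "compare alkaline phosphatase reduction to quantitative imaging techniques".

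The planned size is "Dose escalation N=14; dose expansion N=6 ;total= 20". Table 1 puts 3 patients at 50, 3 at 75 and 8 at 100 kBq/kg, plus 6 at the maximum tolerated dose (MTD), so up to 14 at 100 kBq/kg.

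Under Dose Modification and Escalation, a level is passed with 0 DLTs in 3 patients, or with 1 in the first 3 and none in the next 3. Two or more DLTs stop it.

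The imaging note under Table 1 says "Three modalities will be compared", as delta SUV for the two PET tracers and delta activity for MDP SPECT. Section 8.1 describes per-patient trends and, for imaging, "number of patients in a cohort with improvement after dose #3 and dose #6 will be analyzed"; ALP is handled in the same way by dose number. Section 8.3 refers back to this text. No summary measure, model, interval, threshold for improvement or absolute-versus-relative scale is given.

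**The concern.** The comparison across doses belongs to the primary objective, and a reader will expect a table of DLT rates by dose. The escalation rule makes the passed levels in such a table look alike almost whatever the true rates are.

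For ALP and uptake the stated summary is a count of improved patients in cohorts that may hold 3. This throws away the size of each change. Change written as a delta has different units for SUV, SPECT activity and ALP, so if it means a difference, neither the comparison of modalities nor the comparison with ALP in Section 2.2 has a common scale. The blood counts, ALP and scans are collected anyway, and the plan does not draw on their full content.

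**Working it through.** **Sample size.** Table 1: 3 + 3 + 8 = 14, and 14 + 6 = 20, which reproduces the synopsis. Section 8.5 gives 9 + 6 = 15, which does not match. I use Table 1 and show the alternatives.

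**DLT proportion at a passed level.** With true rate p, let P0 = (1−p)³ and P1 = 3p(1−p)². The level is passed with probability P0 + P1·P0. The mean observed proportion given passing is (1/6)·P1·P0/(P0 + P1·P0).

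| True rate | P0 | P1 | P(passed) | Mean observed |
|---|---|---|---|---|
| 10% | 0.729 | 0.243 | 0.906 | 3.3% |
| 20% | 0.512 | 0.384 | 0.709 | 4.6% |
| 30% | 0.343 | 0.441 | 0.494 | 5.1% |
| 40% | 0.216 | 0.432 | 0.309 | 5.0% |

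The last column is nearly flat over a fourfold range. Exact 95% intervals are 0 to 71% for 0/3 and 0.4 to 64% for 1/6. With 14 patients they are 0 to 23% for 0/14 and 2 to 43% for 2/14.

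**Counts improved.** For 3 versus 3 the smallest two-sided Fisher p is 0.10. For 3 versus 14, against 0/3, it takes 11/14 to fall below 5% (p = 0.029; 10/14 gives 0.0515).

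**Precision with continuous outcomes** (95% half-widths in SD units, complete data).
- Linear dose term, 3/3/14: mean dose 88.75; Sxx = 3(38.75²) + 3(13.75²) + 14(11.25²) = 6843.75; t(18) = 2.101. Per 25 kBq/kg: 2.101 × 25/√6843.75 = 0.63. Between 50 and 100 kBq/kg: 1.27.
- Linear dose term, 3/3/8: 2.179 × 25/√5758.9 = 0.72 per 25 kBq/kg.
- Linear dose term, 3/3/9 (the 15 of Section 8.5, with 100 kBq/kg as the MTD): Sxx = 6000; 2.160 × 25/√6000 = 0.70 per 25 kBq/kg.
- Plain 50 versus 100 kBq/kg, 3 versus 14: 2.131 × √(1/3 + 1/14) = 1.36, or 0.68 per 25 kBq/kg.

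**Continuous values against counts** (assumed: two-sided 5%, normal changes, truly linear effect, 3/3/14). For a true difference of 1 or 1.5 SD between 50 and 100 kBq/kg, the linear term has 35% or 65% power (noncentral t). If improvement is cut so that 31% improve at 50 kBq/kg, then 69% or 84% improve at 100 kBq/kg, and Fisher's test on 3 versus 14 has 11% or 31% power. Moving the cut so that 16% to 60% improve at 50 kBq/kg gives 2 to 14% or 20 to 31%.

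**Scale.** A hypothetical pair: SUV 24 to 22 and SUV 4 to 2 are both −2 as differences, but −8% and −50% as relative change. The ALP results that the protocol cites in Sections 1.3.2 and 4 are relative (a decrease of 66%; a response of at least 30% reduction).

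**The case against.** The plan states no hypothesis test and no 5% level between doses. Section 7.2 calls the indicator-lesion trends exploratory, and descriptive comparison is usual in a 3+3 study. That stands: the power figures rank two ways of using the data and do not show that a planned test fails.

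A reader might infer that the escalation rule fixes the DLT counts, so that neither toxicity nor uptake can be compared between doses. The documents do not support this. The restriction applies at passed levels only. Counts at the stopping dose and in the expansion are free, as are non-DLT toxicity and events after week 6, and the safety set is every treated patient. The rule does not act on uptake. Nor are all groups of size 3, since 100 kBq/kg may hold 8 to 14.

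A reader might also infer that raw differences are prescribed. The text says change or delta without stating absolute or percent, so the fault is an undefined scale.

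Two limits on any remedy also stand. Blood counts are not independent of escalation, because the DLT definition is built partly on anemia, neutropenia and thrombocytopenia. FDG and NaF scans are done only as clinically indicated, and Table 4 requires only the bone scan, so a model for those tracers will not have 20 patients.

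**Conclusion.** The point holds in limited form. DLT proportions at passed levels are almost unrelated to the true rate and cannot support a statement that doses are equally safe. For ALP and uptake, per-cohort counts on an undefined scale are a weaker use of the data than continuous relative change over all dosed patients.

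The gain should not be overstated. The linear model gives 0.63 SD per 25 kBq/kg against 0.68 SD from a plain 3 versus 14 comparison, so most of the benefit comes from continuous values and from including every patient. An interval of ±1.27 SD between 50 and 100 kBq/kg remains wide.

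These figures assume the Table 1 allocation with 100 kBq/kg as the MTD, equal variances and complete data. Later scans will be missing for some patients, and those treated beyond dose 3 are selected by the continuation criteria in Section 6.2.2; the first widens the intervals and the second may bias them. Cohorts are sequential, so dose is confounded with enrolment order. The change is worth making, but the study can describe dose differences only roughly.

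**What to change.** In Sections 2.1, 8.1 and 8.3:

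- **DLTs.** Report proportions by level descriptively with exact 95% intervals, and state that proportions at passed levels are limited by the escalation rule.
- **ALP and each tracer.** Analyse log(follow-up/baseline) as a continuous outcome over all patients with that measurement, including the expansion. Put the required bone scan first; use FDG and NaF only where done, and state the number available.
- **Dose effect.** Fit dose as a linear term with a patient effect for repeated times. Give estimates with 95% intervals, labelled exploratory, and keep cohort counts of improvement as listings.
- **Blood counts.** Summarise platelets, ANC and hemoglobin as log(value/baseline) over the common early window of 2-weekly counts. State that these also feed the DLT definition, so they are more informative than DLT counts but not independent of escalation.
- **Sample size.** Reconcile the 14 + 6 of the synopsis and Table 1 with the 9 + 6 of Section 8.5, since precision depends on it.

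The cost is analysis-plan text and modest programming, with no added assessments. The downsides are an assumed, roughly log-linear dose effect and the confounding with enrolment order, which the report should state.
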